4. ANALYSIS METHODS

4.1 General principles

Statistical analysis will be performed by Wuxi CDS using SAS® Enterprise Guide version 7.1. The below mentioned general principles will be followed throughout the study:

- Descriptive statistics will include number of non-missing subjects (n), number of missing subjects (missing), arithmetic mean (or geometric mean if appropriate), standard deviation (SD), median, quartiles (Q1 and Q3), minimum, and maximum values for continuous variable, and frequency counts and percentages for categorical variables. The 95% CI will be provided when appropriate. Missingness might be summarized as a separate category as applicable. Data will be examined for skewness, outliers, and systematic missing data when appropriate. Transformations will be undertaken as needed.
- For continuous data, arithmetic mean (or geometric mean if appropriate), quartiles (Q1 and Q3) will be rounded to 1 additional decimal place compared to the original data and standard deviation (SD) to 2 additional decimal places compared to the original data. Minimum and maximum will be displayed with the same accuracy as the original data.
- For categorical data, percentages as well as the upper limit and lower limit of 95% CI will be rounded to 1 decimal place.
- Partial date conventions are provided in Appendix 1. Other missing data will not be imputed.
- Target Study day: The initial value of target study day (First Day) is defined as Day 1 of study treatment. The following target study days will be calculated as week x-previous week x.

The end of the treatment is defined as end of NHT, and specifically, the end of treatment effects for Zoladex (12 weeks after last injection, in terms of V4 at 180 ± 10 day). The end of the study is defined as 'the last visit of the subject undergoing the study'. Specifically, for subjects did not undergo RP surgery, the end of study visit will be same as the end of treatment visit. For subjects conducted RP surgery, If one has requested or was requested by the investigator, to quit the study prior to his 90 ± 5 days visit, then an end of study visit should be conducted unless the end of study visit is within 7 days from last scheduled visit. Otherwise his end of study visit will be the 90 day post-surgery visit.

4.1.1 Visit window definition

For treatment period, all post-baseline visits before RP surgery must occur within \pm 5 days from the scheduled date, all regarding assessments should be performed within the specified time window.

Visit post radical operation should be conducted at 180 ± 10 . And if a subject chose not to conduct the RP surgery, the reason should be recorded at the same visit.

For post-surgical follow-up period, all visits must occur within \pm 5 days from the scheduled date. All assessments will be performed within the specified time window.

If multiple readings are recorded within a single visit window, please refer to the rules below.

• If there are 2 or more observations within the same visit window, then the non-missing 1 closest to the visit will be used in the analysis.

- If 2 observations are equidistant from the visit, then the non-missing observation with the earlier collection date will be used in the analysis. If 2 observations are collected on the same day, then the non-missing 1 with the earlier collection time will be included in the analysis.
- If 2 observations are collected on the same day with missing time, the more conservative record will be included in the analysis

4.2 Missing Data Handling Rules

No imputation for missing data will be applied other than those as specified in Appendix 1. All statistical analyses will be primarily carried out on non-missing data.. In presentation of categorical variables, unknown and missing data will be presented as a separate category.

4.3 Analysis methods

4.3.1 Subject disposition

All screened and enrolled subjects will be accounted for in the subject disposition table.

The number and percentage of subjects will be summarized based on following classification:

- Screened
- Screen Failure
- FAS
- Completed Treatment Period
- RPAS
- Completed Study
- Early discontinue from study:
- Reason for early discontinuation:
 - Adverse Event
 - Death
 - Lost to Follow-up
 - Physician Decision
 - Withdrawal by Subject
 - Other

Only reasons with more than 0 subjects recorded will be presented. Specific disposition information will be listed including subject number and completion or discontinuation date

4.3.2 Demographic and baseline characteristics

Demographic and baseline characteristics will be analysed primarily based on FAS.

Demographic variables include following: age, sex, race.

Baseline characteristics including following variables:

- Physical examination variables include following: General appearance, Respiratory, Cardiovascular, Abdomen, Other. Results of each category will be recorded as normal or abnormal, where those did not undergo physical examination will be summarized as "not done".
- The overall evaluation of ECG (in categories as listed: Normal, Non-clinical significant, clinical significant, not done).

Above demographic and baseline characteristics will be analyzed using descriptive statistics as

specified in general considerations section, and listed individually for each subject.

4.3.3 Medical and Surgical history

The Medical and Surgical history will be summarized by per SOC and PT using MedDRA Version 23.0 or above. The number and percentage of subjects with any medical and surgical history as well as each specific term will be summarized by SOC and PT and sorted by descending order of frequencies. Un-coded terms will be summarized as a separate category. All Medical and Surgical history will also be listed individually for each subject.

Above analyses will be performed based on FAS.

4.3.4 Medications and Procedures

The Medications will be presented and coded using WHODrug Global March 1, 2020 or higher version.

See Appendix 1 for handling of partial dates for medications, in the case where it is not possible to define a medication as prior, concomitant, or post treatment, the medication will be classified by the most conersativez case; i.e. concomitant.

- 'Prior' medications are medications which started and stopped prior to the first dose of study medication.
- 'Concomitant' medications are medications which:
 - o started prior to, on or after the first dose of study medication but no later than the end of study medication,
 - AND ended on or after the date of first dose of study medication or were ongoing at the end of the treatment.
- 'Post' medications are medications which started after the end of study medication.

Prior, Concomitant and Post Medications will be listed individually for each subject. The number and percentage of subjects using each medication will be displayed together with the number and percentage of subjects using at least one medication within each therapeutic class (ATC-Level 2) and generic term.

Prior and concomitant Procedures will also be listed individually for each subject. The number and percentage of subjects using each procedure will be displayed together with the number and percentage of subjects using at least one procedures.

Previous/current cancer therapy and previous/current radiotherapy will be summarized using same method as described above.

Above analyses will be performed based on FAS.

4.3.5 Exposure

4.3.5.1 Study Medication Exposure

Exposure to investigational product (Zoladex or Casodex) i.e., dosage of study drug and duration of exposure (days) will be summarized and listed individually for each subject by Zoladex and Casodex separately.

For Zoladex, the number of injection will be summarized as continuous variable. While for Casodex, total dosage, daily dose and duration will be summarized. Number and percentage of subjects with at least one dose interruption/delay record and with at least one dose reduction record will be

summarized as well.

For Casodex:

Duration of exposure (days) = date of last dose of Casodex taken – date of first dose of Casodex taken – days of Casodex not taken+ 1.

Above analyses will be based on FAS.

4.3.5.2 Study Medication Compliance Rate

Study medication compliance rate will be summarized by Zoladex and Casodex, where both compliance rate will be summarized as continuous variables by Casodex and Zoladex. Each subject's expected tablets/implants and actual tablets/implants as well as the ratio between them (in form of percentage) will be listed.

4.3.6 Analysis of the primary variable (s)

The number and percentage of subjects received radical prostatectomy after NHT will be summarised with 95% confidence interval provided.

4.3.7 Analysis of the secondary variable(s)

4.3.7.1 PSA level, mean PSA level by the end of NHT, resection margin status, seminal vesicle invasion, involvement of bilateral pelvic lymph nodes ,pathological downstaging and rate of post-surgical PSA decreased to less than 0.1ng/ml

PSA level will be summarized by visit, and change from baseline value will be summarized for post-baseline visits. PSA level and average PSA level by the end of NHT will be analysed based on FAS. While other variables will be summarized using descriptive statics based on RP analysis set. Shift table for pathological stage between baseline and post-surgery assessment might be provided as applicable.

4.3.7.2 Surgical variables and complications

- Operative Duration and Intraoperative Estimated Blood Loss will be summarized as continuous variables. Reasons for not performing RP will be summarized by category. For duration of Indwelling Catheterization (Days), summary statistics will be calculated based on those who had non-missing indwelling catheter end date, as count and percentage of missingness will be summarized separately.
- Complications

The number and percentage of subjects with any complications and any complications needing intervention will be summarized by SOC and Preferred Term (PT) for RP analysis set. All information of radical prostatectomy related complications including start/stop date and outcome will be listed individually for each subject.

4.3.7.3 Urine Function and Erectile function

- Urinary rate and erectile rate at 12 weeks after surgery will be calculated with 95% confidence interval provided. Denominator will be based on RPAS where percentage of subjects with missing records will be reported as a separate category.
- Time to continence (in Days) will be summarized as continuous variable. Median time to continence will be estimated using Kaplan-Meier method and a Kaplan-Meier plot might be

provided as applicable. Subjects who remained incontinence or with missing urine function records will be censored at his latest visit day with non-missing urine function record. Subjects with no post-surgery records will be censored at day 1.

4.3.7.4 Adverse events(AEs)

Treatment-emergent AEs (TEAEs) are defined as the AEs occurring on or after the first dosing of study drug and up to 4 weeks after discontinuation of study drug. All AEs will be listed and summarized. See Appendix 1 for handling of partial dates for AEs, in the case where it is not possible to define TEAEs, the AEs will be identified as TEAEs.

AEs will be categorized into one or more of the following categories depending on the type of events reported:

- AEs
- SAEs
- Treatment-emergent AEs,
- Drug-related AEs (Zoladex related, Casodex related)
- Drug-related SAEs
- AEs leading to study drug discontinuation
- AEs with an outcome of death
- AEs of CTCAE Grade 3 or higher

An overall summary of the number and percentage of subjects in each category will be presented, as will an overall summary of the number of events in each category.

The number and percentage of subjects with TEAEs in each category above will be summarized and events in each category will be further summarized by MedDRA SOC and PT.

All related information (such as SOC/PT, CTCAE Grade, outcome, etc.) about adverse event will be listed for each subject and each term, based on following category: Deaths, SAEs and AEs. Above analyses will be performed based on FAS.

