4 STUDY PLAN AND TIMING OF PROCEDURES

4.1 Study schedule

Visit	1	2	3	4	5 ^e	6	7	8 ^g	For
Day	-28 to -1	1	85	169/E nd of treatm ent	EOT+30	RP+30	RP+90	Study completio n/disconti nuation	details see Protocol Section
Visit window	_	±5d	±5d	±5d		±5d	±5d	±5d	
Written informed consent	X								4.2
Demographics	X								4.2
Physical examination	X	Xa							4.2
Medical/surgical history	X								4.2
Inclusion/exclusion criteria	X								4.2
ECOG performance status	X	Xa	X	X	Xª		X	X	4.2, 4.3 & 4.4
Vital signs, body weight	X	Xa	X	X	Xª		X	X	4.2
ECG	X	Xa			Xa				4.2
Imaging (CT or MRI)	x					X (clinical ly indicated)	X (clinical ly indicated)	X (clinical ly indicated)	4.2, 4.3 & 4.4
Bone scan	X								4.2, 4.3 & 4.4
Gleason score	X				X				4.2 & 4.4
Zoladex and Casodex treatment		Xc	Xc						4.3
RP evaluation				X					4.3
RP					X				4.4
Assessment after radical prostatectomy plus ePLND					X				4.4
ADT after RP						X ^b	Xb	X ^b	4.4

Visit	1	2	3	4	5°	6	7	8 ^g	For
Day	-28 to -1	1	85	169/E nd of treatm ent	EOT+30	RP+30	RP+90	Study completio n/disconti nuation	details see Protocol Section
Visit window	-	±5d	±5d	±5d		±5d	±5d	±5d	
Concomitant medication	X	X	X	X	X	X	X	X	4.2, 4.3 & 4.4
Adverse event	X	X	X	X	X ^d	X ^d	X ^d	X ^d	4.3 & 4.4
Haematology and clinical chemistry	X	Xa	X	X		X	X	X	4.2, 4.3 & 4.4
Blood germline forHRRm collected				X(all patien ts)					4.3
Tumor tissue for HRRm collected					X ^h				4.4
Urinalysis	X	Xa							4.2
Serum testosterone level	X	Xa	X	X		X	X	X	4.2, 4.3 & 4.4
Serum PSA level	X	Xa	X	X		X	X	X	4.2, 4.3 & 4.4

a. If assessed within 7 days before enrolment and meets the stated eligibility criteria (if applicable), it does not need to be repeated on Day 1 of study treatment unless investigator believes that it is likely to have changed significantly.

b. The treatment will be based on investigator's discretion

c. Casodex will be administrated till Week 24

d. AEs will be actively collected from ICF to 12 weeks after last dose of Zoladex

e. Radical prostatectomy should be performed within 30 days after end of NHT. The visit will be ended for the patients without radical operation following NHT after collection of the reason for failure to receive an operation.

f. The visit will be completed after follow-up for three months following radical operation

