6.4.3 Variables

The following variables will be collect for each AE:

- AE (verbatim)
- The date and time (if applicable) when the AE started and stopped
- max CTCAE grade
- Whether the AE is serious or not
- Investigator causality rating against the IP (yes or no)
- Action taken with regard to IP
- Outcome.

In addition, the following variables will be collected for SAEs:

- Date AE met criteria for serious AE
- Date Investigator became aware of serious AE
- AE is serious due to
- Date of hospitalization (if applicable)
- Date of discharge (if applicable)
- Probable cause of death (if applicable)
- Date of death (if applicable)
- Autopsy performed (yes or no; if yes provide report) (if applicable)
- Causality assessment in relation to Study procedure(s)
- Description of AE.

It is important to distinguish between serious and severe AEs. Severity is a measure of intensity whereas seriousness is defined by the criteria in Section 6.2. An AE of severe intensity need not necessarily be considered serious. For example, nausea that persists for several hours may be considered severe nausea, but not a SAE unless it meets the criteria shown in Section 6.2. On the other hand, a stroke that results in only a limited degree of disability may be considered a mild stroke but would be a SAE when it satisfies the criteria shown in Section 6.2.

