1.1.2 Secondary objectives

- To investigate the efficacy of NHT before radical prostatectomy (RP) in subjects with locally advanced prostate cancer by assessment of PSA, percentage of positive surgical margin for primary tumor, incidence of seminal vesicle invasion and involvement of bilateral pelvic lymph nodes.
- To observe surgical-related variables and complications.
- To evaluate the safety of NHT using goserelin and bicalutamide.

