7. APPENDIX 1: PARTIAL DATE CONVENTIONS

Imputed dates will NOT be presented in the listings.

Algorithm for Treatment-emergent Adverse Events:

START DATE	STOP DATE	ACTION
Known	Known/Partial/Missing	If start date < study treatment start date, then not TEAE
		If start date >= study treatment start date, then TEAE
Partial, but known	Known/Partial/Missing	Not TEAE
components show that it cannot be on or after study treatment start date	, , , , , , , , , , , , , , , , , , , ,	
Partial, could be on or after study treatment start date	Known/ Partial/Missing	Impute stop date as latest possible date (i.e. last day of month if day unknown or 31st December if day and month are unknown), if partial or missing date exist.
		If stop date < study treatment start date, then not TEAE
		If stop date >= study treatment start date, then TEAE
Missing	Known/ Partial	Impute stop date as latest possible date (i.e. last day of month if day unknown or 31st December if day and month are unknown), if partial or missing date exist.
		If stop date < study treatment start date, then not TEAE
		If stop date >= study treatment start date, then TEAE
	Missing	Assumed TEAE

Algorithm for Prior / Concomitant Medications:

START DATE	STOP DATE	ACTION
Known	Known	If stop date < study treatment start date, assign as prior If stop date >= study treatment start date and start date <= end of treatment+3 months, assign as concomitant If start date > end of treatment+3 months, assign as post study
	Partial	Impute stop date as latest possible date (i.e. last day of month if day unknown or 31st December if day and month are unknown), then: If stop date < study treatment start date, assign as prior
		If stop date >= study treatment start date and start date <= end of treatment+3 months, assign as concomitant If start date > end of treatment+3 months, assign as post treatment
	Missing	If start date > end of treatment+3 months, assign as post treatment If start date > end of treatment+3 months, assign as post treatment If start date > end of treatment+3 months, assign as post treatment
Partial	Known	Impute start date as earliest possible date (i.e. first day of month if day unknown or 1st January if day and month are unknown), then: If stop date < study treatment start date, assign as prior If stop date >= study treatment start date and start date <= end of treatment+3 months, assign as concomitant If start date > end of treatment+3 months, assign as post treatment

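### The all-cause adverse event tables in SAP 4.3.7.4 can mix hormone-period and post-operative events, because nothing divides them at the date of prostatectomy

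*SAP*

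**What the plan says.** The safety objective in SAP 1.1.2 is "To evaluate the safety of NHT using goserelin and bicalutamide"; protocol 2.2 has the same objective.

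**Tables.** SAP 4.3.7.4 defines treatment-emergent events (TEAEs) as those "occurring on or after the first dosing of study drug and up to 4 weeks after discontinuation of study drug". It lists eight categories: AEs, SAEs, TEAEs, drug-related AEs by product, drug-related SAEs, AEs that led to stopping study drug, fatal AEs, and AEs of grade 3 or higher. It then says "The number and percentage of subjects with TEAEs in each category above will be summarized", and closes with "Above analyses will be performed based on FAS". There is no split at the RP date and no procedure-related category.

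**Algorithm.** For an event with a known start date, SAP Appendix 1 says "If start date >= study treatment start date, then TEAE". It sets no end.

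**Surgery.** Protocol 4.1, footnote e: "Radical prostatectomy should be performed within 30 days after end of NHT". Protocol 6.1 excludes only the operation from being an AE, not its complications. SAP 4.3.7.2 plans a separate output, in which "subjects with any complications and any complications needing intervention will be summarized by SOC and Preferred Term (PT) for RP analysis set".

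**Collection.** Protocol 6.4.1, 6.5 and footnote d of 4.1 limit active AE and SAE collection to the period from consent to 12 weeks after the last Zoladex dose. The AE row of the schedule is nevertheless marked up to Visit 8 under that footnote, and protocol 4.4 lists adverse events among the items collected at Visit 5, the surgery visit. Protocol 6.4.3 and 6.4.4 record, for every SAE, a causality assessment against study procedures as well as against the investigational product.

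**The concern.** The trial has one arm, so no control group shows what prostatectomy with lymph node dissection contributes to the event counts. The operation comes directly after drug treatment. Any post-operative event that is recorded as an AE enters the same all-cause TEAE, SAE, grade 3+ and death counts as events on goserelin and bicalutamide. How many such events enter depends on when a man stopped treatment and when he was operated, which says nothing about drug toxicity.

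Anaemia is an example. Protocol 6.10 lists decreased haemoglobin among the abnormalities reported with Casodex plus an LHRH analogue, and blood loss is a planned surgical outcome. A pooled count cannot separate the two sources. The SAP also does not say whether an RP complication is entered as an AE as well. If it is, one event appears twice, once on the FAS denominator and once on the RPAS denominator.

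**Working it through.** The plan gives no figure on this point, so the check is day arithmetic on the protocol schedule.

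**Inputs**
- Zoladex on Day 1 and Day 85; visit window ±5 days; end-of-treatment visit on Day 169 (protocol 4.1).
- Casodex until Week 24, so the last tablet is on about Day 24 × 7 = 168 (protocol 4.1, footnote c).
- RP within 30 days after the end of NHT (footnote e).
- Active collection to last Zoladex + 84 days (protocol 6.4.1).
- TEAE window to drug discontinuation + 28 days (SAP 4.3.7.4).

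**Man treated on schedule**

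Possible RP days are 169 + 1 = 170 to 169 + 30 = 199, which is 30 days.

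| Limit | Last day | Possible RP days covered |
|---|---|---|
| TEAE window, clock from last Casodex | 168 + 28 = 196 | 170–196: 27 of 30 |
| TEAE window, clock from last implant | 85 + 28 = 113 | 0 of 30 |
| SAP Appendix 1, known start date | none | 30 of 30 |
| Active AE collection | 85 + 84 = 169 | 0 of 30 |

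The first three rows show which events would be flagged as TEAEs if they were recorded. The fourth shows what sites must actively record. In this man, active collection has closed before the first possible operation day.

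SAP 4.1 adds one more reading. It places the end of treatment at Visit 4 on Day 180 ± 10, against Day 169 ± 5 in the protocol. Counted from there, the 28 days end between 170 + 28 = Day 198 and 190 + 28 = Day 218.

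**Routes by which post-operative events still enter**
1. *Visit-window shifts.* With the second implant on Day 90, collection runs to 90 + 84 = Day 174. That is 5 days past an end-of-treatment visit on Day 169, and 10 days past one on Day 164.
2. *Early stoppers who are operated.* SAP 3.1 and the RPAS definition in protocol 8.3 both include them. Their whole 30-day RP period lies inside active collection if stop day + 30 is no later than the end of collection. With one implant, collection ends on 1 + 84 = Day 85, so this holds for stops up to 85 − 30 = Day 55. With two implants it holds for stops up to 169 − 30 = Day 139.
3. *Visit 5.* Protocol 4.4 lists adverse events for collection there.
4. *Later SAE notification.* Protocol 6.4.1 lets the investigator notify an SAE after the window if it is considered related to study treatment or study participation.

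An event recorded by any route counts in the AE and, if serious, SAE categories of the overall summary. With a known start date on or after first dose, Appendix 1 also flags it as a TEAE whatever the date of surgery.

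**The case against.** The case on the other side is substantial.
- An all-cause table counts occurrence and attributes nothing. Every AE carries an investigator rating against the investigational product, and SAP 4.3.7.4 plans separate drug-related AE and SAE categories.
- Surgical complications have their own MedDRA-coded table on the RPAS and a dated listing. Erectile function has its own 12-week analysis.
- For a man on schedule, active collection closes at about the time surgery becomes possible.
- The SAP categories cover those in protocol 8.5.2. Neither document promises a procedure-related table, and SAEs are listed subject by subject.
- Judging NHT safety only on pre-RP events would lose drug effects that begin after surgery, and would give non-operated men a longer observation period.

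Much of this stands. A reader might infer that surgical events are being reported as the safety of NHT. The documents do not support that, because the drug-related categories and the complication table exist. A reader might also take the 27 of 30 days to mean that most completers' early post-operative events will be counted. That figure describes the flagging window, not what is collected. Nor does any text say that a complication is also entered as an AE, so double counting is possible but not shown.

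What does not stand is that these outputs settle the matter. None of them removes a surgical event from the all-cause tables. The drug-related tables rest on a yes/no judgement without a control arm. Protocol Appendix A tells investigators to treat ambiguous cases as reasonably possible, although it also says that a more likely alternative cause points the other way. The last objection is accepted, and it is why the fix keeps the pooled tables and counts drug-related events from both periods.

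**Conclusion.** The point holds in limited form. The all-cause AE, TEAE, SAE, grade 3+ and death tables can mix hormone-period and post-operative events. Neither version of the TEAE period ends at RP, and the procedure causality collected for SAEs is never tabulated. The extent cannot be computed, because the documents give no AE or complication rates. It is probably limited for on-schedule completers and falls mainly on early stoppers who are operated, visit-window shifts, Visit 5 entries and SAEs notified later.

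This rests on two assumptions: that the last tablet is on about Day 168 in a man on schedule, and that sites follow the 12-week limit. If sites record events at Visits 5 to 8 despite footnote d, the mixing is larger. The primary endpoint is unaffected; a stated secondary objective is affected. The change is worth making because it is specific and uses data already collected.

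**What to change.** In SAP 4.3.7.4 and Appendix 1:
1. Keep the pooled tables. Add a presentation of TEAEs, SAEs, grade 3+ events and deaths by onset before RP (FAS, with non-operated men over their whole TEAE period) and on or after RP (RPAS).
2. State that the all-cause safety of NHT is read mainly from the pre-RP period, together with drug-related events from both periods.
3. Add a category for SAEs related to study procedure, from the causality item already collected, and state that RP counts as a study procedure for that item.
4. State whether RP complications are also counted as AEs.
5. Put the TEAE end limit into Appendix 1, and say which drug's discontinuation starts the four-week clock.

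The two documents should also reconcile the four-week TEAE limit, the 12-week collection period, the AE entries at Visits 5 to 8, and the end of treatment on Day 169 versus Day 180 ± 10.

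The cost is SAP wording and one onset-period flag in programming, with no new data. Protocol 8.1 allows SAP amendments up to data lock. The downsides are a few more tables with smaller counts, and unequal observation time between operated and non-operated men in the pre-RP table, which a footnote should state.
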